7 RULES FOR INTERPRETATION OF ANALYSIS

No formal statistical analyses are planned; therefore there is no rule for the interpretation of results for this study.

The ongoing data listings included in Appendix III will be prepared by the statistical team at Cangene Corporation, and provided to the medical monitor every month for ongoing safety monitoring. Additional ongoing listings and summary tables may be required for the centralized monitoring purpose.

Statistical team at Cangene Corporation will also provide support on the centralized monitoring. The following aspects may be reviewed remotely for each site:

- Timeliness and completeness of entering initial subject data
- Enrollment status
- Days since last entering of data into EDC vs. expected entered data
- Missing data
- Number of queries
- Query Status
- Data error rates
- Protocol deviations/violations
- Number of AEs/SAEs
- Percentage of Screen Failures

Any concerns raised by monitoring requires additional subjects or additional percentage of information to be monitored at the site, the additional subjects will be randomly selected by Biostatistician at Cangene Corporation.

An independent DSMB will review the study data on a regular basis. The first DSMB meeting following the DSMB organizational meeting will be held after the initial fifty (50) subjects have reached Day 28 and this milestone will mark the commencement of the DSMB annual meetings thereafter. The whole safety data package predefined in the appendices will be provided to the DSMB meeting for review. This data package will include all information available as of the cut-off date. If at any point in the study, there are any signals indicative of potential safety concerns, additional data package will be provided to the DSMB for an ad-

hoc meeting as required. An ad-hoc meeting will occur if the one of the following situations has occurred:

1. In the event that either one related SAE is reported and/or two subjects with related unexpected (assessed as severe as per section 7.5 of the protocol) AEs occur.
 - Complete information on the known AE profile of ACAM2000 is documented in the Investigator's Brochure.
2. As described in Investigator's Brochure: In the ACAM2000 clinical studies 92% of previously vaccinated subjects, experienced one or more adverse event. Common events included injection site reactions (erythema, pruritus, pain and swelling) and constitutional symptoms (fatigue, malaise, feeling hot, rigors and exercise tolerance decreased). Across all ACAM2000 studies 3% of previously vaccinated subjects experienced at least one severe adverse event (defined as interfering with normal daily activities). In the event that 6% of vaccinated subjects report related expected AEs assessed as severe as per section 7.5 of the protocol an ad hoc DSMB meeting will occur.
3. If two pregnancies occur during the study.
 - ACAM2000 has not been studied in pregnant women. Live vaccinia virus vaccines can cause fetal vaccinia and/or fetal death.
 - Note: One pregnancy will result in a Cangene Corporation directed investigation, corrective actions and a Dear Investigator Letter to all study sites as noted in the VA-008 Medical Monitoring Plan.
4. If two secondary transmissions occur during the study.
 - ACAM2000 is a live vaccinia virus that can be transmitted to persons who have close contact with the vaccinee and the risks in contacts are the same as those stated for vaccinees.

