7 MANAGEMENT AND REPORTING OF ADVERSE EVENTS/ADVERSE REACTIONS

The Principal Investigator is responsible for the evaluation and documentation of events meeting the criteria and definition of an adverse event (AE)/adverse drug reactions (ADR) or serious adverse event/reactions (SAE/SAR) as provided in this protocol.

All AEs are to be elicited by the Principal Investigator. The causality relationship of an AE with the study drug is to be determined by Principal Investigator.

Diary cards will be utilized to help subjects record and track AEs between study assessments. All adverse events/reactions on diary cards will be reviewed with subjects by the Principal Investigator and/or designate at the regularly scheduled visits. The reviewer will sign the diary card to document this review. If unable to sign the diary card, the Principal Investigator will document review of the diary card in the corresponding visit source document. If the subject is unable to attend in person, an image of the diary card will be transmitted to the Principal Investigator by photo or live video call. If possible, an image of the diary card will be printed and filed in the subject's source document file. Adverse events from the diary card will then be entered into the electronic case report form (eCRF) that is within data capture (EDC) system.

All adverse events/reactions will be examined by the investigator for assessment of both severity and causality using the criteria described in sections [7.6](#) and [7.7](#).

The definitions for adverse events/adverse drug reactions, as well as serious events/reactions provided below follow definitions provided by ICH, 21 CFR 312 and Office for Human Research Protection (OHRP) Guidance documents.

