7.5 Serious Adverse Events

An AE should be classified as a SAE if it meets one of the following criteria:

- Results in death.
- It is life-threatening. An event is considered life-threatening if, in the view of the physician or healthcare provider, its occurrence places the subject at immediate risk of death at the time of the event; it does not refer to an event that hypothetically might have caused death if it was more severe.
- Requires inpatient hospitalization or prolongation of existing hospitalization.

Note: complications that occur during hospitalization are AEs. If a complication prolongs hospitalization or fulfills any other serious criteria, the event is considered serious. Any stable condition for which hospitalization is planned before study inclusion or in-hospital treatment as outpatient is not considered an SAE. Hospitalization during the study for social reasons (transport difficulties, respite, etc.) or observation in the emergency room for no more than 24 hours is not considered an SAE.

Emergency room visits that do not result in admission to the hospital should be evaluated for one of the other serious outcomes (e.g., life-threatening; required intervention to prevent permanent impairment or damage; other serious medically important event).

- Results in persistent or significant disability or incapacity. The term disability is defined as substantial disruption of a person's ability to conduct normal life functions, physically or mentally. This definition is not intended to include experiences of relatively minor medical significance, such as uncomplicated headache, nausea, vomiting, diarrhea, influenza, or accidental trauma (e.g., sprained ankle) that may interfere with or prevent everyday life functions but do not constitute a substantial disruption.
- Constitutes a congenital anomaly or birth defect.
- Any other medically significant event. Any other medically significant event includes an important medical event that may not be immediately life threatening or result in death or hospitalization but may jeopardize the subject and may require medical or surgical intervention to prevent one of the other outcomes listed in the definition above. Examples of such events include intensive treatment in an emergency room or at home for allergic bronchospasm; blood dyscrasias or convulsions that do not result in hospitalization; or development of drug dependency or drug abuse.

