7.6 Assessment of Severity (intensity)

Assessments of AE/ADR severity are to follow the guidelines provided below:

Table 1 AE/ADR Severity Assessment

Intensity	Description
Mild	Awareness of a sign or symptom but subject can tolerate.
Moderate	Discomfort enough to cause interference with normal daily activity.
Severe	Resulting in an inability to do work or do usual daily activity.

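### Ad-hoc DSMB triggers 1 and 2 define severe by protocol section 7.5, which defines seriousness; severity is graded in section 7.6, and the 3% beside the 6% trigger is not shown to be on the same scale

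*SAP*

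**What the plan says.** SAP section 7 lists four situations in which an ad-hoc DSMB meeting will take place. Two depend on severity.

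- Trigger 1: "either one related SAE is reported and/or two subjects with related unexpected (assessed as severe as per section 7.5 of the protocol) AEs occur".
- Trigger 2: "In the event that 6% of vaccinated subjects report related expected AEs assessed as severe as per section 7.5 of the protocol".

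Just before trigger 2, the SAP cites the Investigator's Brochure for background: across the ACAM2000 studies, "3% of previously vaccinated subjects experienced at least one severe adverse event (defined as interfering with normal daily activities").

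Protocol section 7.5 is the definition of a serious adverse event: "An AE should be classified as a SAE if it meets one of the following criteria". Protocol section 7.6 is the severity section: "Assessments of AE/ADR severity are to follow the guidelines provided below". Its Table 1 describes Moderate as "Discomfort enough to cause interference with normal daily activity" and Severe as "Resulting in an inability to do work or do usual daily activity".

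The other two triggers (two pregnancies, two secondary transmissions) do not depend on severity and are not affected.

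**The concern.** Seriousness and severity are different attributes of an adverse event. A reaction can stop someone working for a day without meeting any seriousness criterion. These triggers are the only mandatory, countable rules on severity that bring the DSMB together between its annual meetings. If they point to the wrong definition, whoever applies them cannot tell from the SAP which events to count.

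What is at stake is a missed or late ad-hoc meeting about related, severe, non-serious reactions. No stopping decision, estimate or test depends on it, since the SAP plans no formal analysis.

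A second question arises once the reference is corrected. The 3% is the only severe-event rate given near the 6%, so a reader will naturally take it as the background. That is safe only if both percentages count the same kind of event.

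**Working it through.** **Inputs.** Triggers 1 and 2, the 3% and the first DSMB milestone of 50 subjects: SAP section 7. Seriousness criteria: protocol 7.5. Severity grades: protocol 7.6, Table 1. Enrolment of about 750 to 3000: protocol 8.1. Document versions: the SAP is v1.0 of June 2015, according to the note filed with it; the protocol is v2.6 of June 2020.

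**Step 1: where the protocol grades severity.** Section 7.5 lists outcomes such as death, threat to life, hospital admission, disability and birth defect, and contains no intensity grade. The protocol sends severity elsewhere consistently. The opening of section 7 has every event examined "for assessment of both severity and causality using the criteria described in sections" 7.6 and 7.7. Section 7.3 also points to 7.6 for severity, section 7.1 cites 7.5 for seriousness, and section 3.4 has the investigator assess seriousness and intensity as separate items. The reference to 7.5 is therefore wrong against the current protocol. The 2019 note filed with the SAP deals with re-enrolment and does not correct it.

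**Step 2: what the literal reading does.** Let S be the set of related events that meet section 7.5. Every event in S is a related SAE. The first limb of trigger 1 fires at one related SAE, expected or unexpected.

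- The second limb of trigger 1 needs two subjects with unexpected events in S. It cannot be met before the first limb.
- Trigger 2 needs ceil(0.06 × n) subjects with expected events in S:

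| n vaccinated | 0.06 × n | Subjects for trigger 2 | Related SAEs for trigger 1 |
|---|---|---|---|
| 16 | 0.96 | 1 | 1 |
| 50 | 3 | 3 | 1 |
| 750 | 45 | 45 | 1 |
| 3000 | 180 | 180 | 1 |

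Trigger 2 never fires before trigger 1. On this reading, both severity rules reduce to one related SAE, and related events that are severe but not serious count toward nothing.

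**Step 3: the 3% and the 6% if section 7.6 is meant.** The plan gives no derivation of the 6%. Arithmetically 6% / 3% = 2, but the SAP does not say that the trigger is a doubling of the background.

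| Attribute | 3% (as quoted) | 6% trigger |
|---|---|---|
| Severity | interference with daily activities | Table 1 Severe: inability |
| Causality | none stated | related only |
| Expectedness | none stated | expected only |

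The severity wording of the 3% is close to Table 1 Moderate. Protocol 7.8.1 agrees, since it treats mild reactions as ones that leave daily function intact, which puts the start of interference just above Mild. The expectedness limit is not itself a fault, because related unexpected severe events are handled by trigger 1 at two subjects.

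**Step 4: illustration only.** Suppose a single look at n = 50, where trigger 2 needs X ≥ 3, with X binomial(50, p) and p the unknown true rate of countable events.

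For p = 3%: P(X ≥ 3) = 1 − 0.97^50 − 50 × 0.03 × 0.97^49 − 1225 × 0.03² × 0.97^48 = 1 − 0.218 − 0.337 − 0.255 = 0.189 (from unrounded terms).

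The same formula gives 1.4% at p = 1%, 3.9% at 1.5%, and 58.4% at 6%. The documents supply no p for related, expected, Table 1 Severe events, so these figures show only that the trigger's behaviour depends heavily on a rate the SAP does not give. They do not measure an effect of the mismatch.

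**The case against.** The strongest reply is that the reference is a numbering slip that nobody would follow. Both triggers speak of events assessed as severe, the next section of the protocol is the severity section, and the redundancy of the literal reading itself shows that severity was meant. The SAP predates protocol v2.6 by about five years, and 7.5 may have been correct in an earlier protocol; that cannot be checked here. This is a good argument about intent, and I accept that 7.6 was probably meant. It does not make the current text right, and a mandatory safety rule should not rely on its user to infer the definition.

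Second, other cover exists. The SAP allows data to go to the DSMB for an ad-hoc meeting on any sign of a safety concern, the medical monitor receives listings every month, and any related SAE fires trigger 1. The DSMB Charter, which is not among the documents, may state the triggers correctly. All of this stands and limits the consequence. The signal clause and the monthly review, however, rest on judgement and set no count for severe non-serious events.

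Third, the 3% is a paraphrase of an Investigator's Brochure that is also not supplied. Inability is a form of interference, so the source studies may have used a top grade; silence on causality does not establish that all causes were counted. The trial counts possibly related events as related, so that limit may remove few reactions. This stands, and it is why the second point carries lower confidence.

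A reader might infer that the trigger is less sensitive than the 3% suggests, since its definition looks narrower. The documents do not support that. How events were collected in the source studies is unknown, while this trial uses diary cards, repeated visits and a Day 90 assessment, which could push the observed rate the other way.

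**Conclusion.** The cross-reference is wrong as written in both triggers; confidence is high. On the literal reading, the second limb of trigger 1 and all of trigger 2 add nothing to the rule of one related SAE, and related, severe, non-serious reactions have no mandatory ad-hoc trigger between annual DSMB meetings. This should be fixed. The practical exposure is limited to delay, and is reduced by the general signal clause and monthly review.

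The second point holds with lower confidence and in a limited form: as quoted, the 3% and the 6% are not shown to be on the same scale of severity or causality. It would be tempting to conclude that 6% was set by doubling a mismatched 3%, or that 6% is too high. Neither follows. The SAP states no derivation, and the direction and size of any effect on sensitivity cannot be established from the documents. The binomial figures rest on assumed rates and a single look; the SAP does not say how often the 6% is checked or from what number of subjects.

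**What to change.** 1. In triggers 1 and 2 of SAP section 7, replace the reference to section 7.5 with section 7.6, Table 1. Keep the split between unexpected events (trigger 1) and expected events (trigger 2).
2. Check that the DSMB Charter uses the same definition.
3. Look up in the Investigator's Brochure how the 3% was graded and whether it was limited by causality. State this beside the figure, reconcile it with the trigger's numerator, and confirm or restate the 6% with its rationale.

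The cost is SAP wording, one look-up in the Brochure and one check of the Charter. No new data are needed. Once the triggers count severe non-serious events, some additional ad-hoc meetings are possible; how many depends on a background rate and a checking schedule that the SAP does not give.

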APPENDIX I SUMMARY TABLES AND FIGURES

Summary tables and figures are numbered according to ICH E3. The following is a list of table numbers and titles that will be included as summary tables in the clinical study report section 14. Additional tables may be added to section 14 at the request of the clinical study report authors.

14.1 Demographic Data

14.1.1 Summary of baseline demographic and other characteristics

14.2 Efficacy Data N/A

14.3 Safety Data

14.3.1 Displays of Adverse Events

14.3.1.1 Adverse events by system organ class and preferred term

14.3.1.2 Adverse events by system organ class, preferred term and relatedness

14.3.1.3 Adverse events by system organ class, preferred term and intensity

14.3.1.4 Adverse events by system organ class and preferred term with incidence $\geq 5\%$ ¹

14.3.1.5 Serious adverse events by system organ class and preferred term²

14.3.1.6 Serious adverse events by system organ class, preferred term and relatedness²

14.3.1.7 Serious adverse events by system organ class, preferred term and intensity²

14.3.1.8 Serious adverse events by system organ class and preferred term with incidence rate $\geq 5\%$ ²

14.3.1.9 Related adverse events by system organ class, preferred term and intensity

14.3.2 Listing of deaths and other serious adverse events

14.3.3 Narratives of death and other serious adverse events

14.3.4 Summary of laboratory values

14.3.4.1 Summary of blood chemistry results

14.3.4.2 Summary of hematology results

14.3.4.3 Summary of out-of-range blood chemistry test results

¹ This table will be generated if at least one adverse event is experienced by at least 5% of subjects.

² This table will only be generated if a sufficient number of SAEs are recorded.

- 14.3.4.4 Summary of out-of-range hematology test results
- 14.3.4.5 Summary of incidence of abnormal EKG results
- 14.3.4.6 Summary of vital signs over time
- 14.3.4.7 Summary of pregnancy test results

APPENDIX II SAS OUTPUTS

As there are no efficacy analyses described in the statistical analysis plan, no statistical methods were used in the analysis of data. Section 16.1.9 Documentation of Statistical Methods of the Clinical Study Report will contain the Statistical Analysis Plan but will not contain any SAS output.

APPENDIX III DATA LISTINGS

The following listings are to be included in the clinical study report section 16.2 Patient Data Listings. Additional listings may be added to section 16.2 at the request of the clinical study report authors. Data listings are numbered in accordance with ICH E3.

16.2.1 Discontinued subjects

16.2.1.1 Listing of discontinued subjects

16.2.2 Protocol deviations

16.2.3 Patients excluded from the efficacy analysis N/A

16.2.4 Demographic Data

16.2.4.1 Listing of demographic and other baseline characteristics

16.2.4.2 Listing of medical history

16.2.4.3 Listing of smallpox vaccination history

16.2.5 Compliance and/or drug concentration data

16.2.5.1 Listing of screening failures

16.2.5.2 Listing of inclusion/exclusion criteria

16.2.5.3 Listing of vaccine administration

16.2.6 Individual efficacy response data N/A

16.2.7 Adverse event listing

16.2.7.1 Listing of adverse events

16.2.7.2 Listing of related adverse events

16.2.7.3 Listing of peri/myocarditis assessments

16.2.7.4 Listing of vaccination site inspection

16.2.8 Listing of individual laboratory measurements by subject

16.2.8.1 Listing of blood chemistry test results

16.2.8.2 Listing of hematology test results

16.2.8.3 Listing of assessment of childbearing potential and pregnancy test results

16.2.8.4 Listing of immunologic assessments

16.2.8.5 Listing of EKG results

16.2.8.6 Listing of HIV serology results

16.2.9 Additional Data Listings

16.2.9.1 Listing of concomitant medications

16.2.9.2 Listing of vital signs

16.2.9.3 Listing of comment log

Protocol No. / Title: VA-008 / Vaccinia Vaccination (ACAM2000®) of Plasma Donors for the Production of Vaccinia Immune Globulin Intravenous (VIGIV), Amendment 2.5

Site Code: N/A

Investigator: N/A

TMF Section/Artifact Name: 1.7.7 Statistical Analysis Plan

Date: 2019Jul24

Details: Protocol Amendment 2.5 dated 2019-Feb-08 permitted re-enrollment of study subjects as detailed in Section 4.3.4, below.

4.3.4 Subject Re-Entry into the Study

Subjects who have been previously vaccinated with ACAM2000 in VA-008 may be eligible to re-enter the study after three years providing that subjects meet all eligibility and screening requirements.

The statistical analysis plan (SAP) version 1.0 dated 2015Jun10 and the associated table and listing shells version draft 0.2 dated 2015May15 did not provide for subjects to enroll in the study more than once. For example, the demographic table counts each subject once in descriptive statistics of age, gender, race, ethnicity, height, weight and body mass index. In order to avoid double counting of the same subject, the subsequent enrollment record for a re-enrolled subject would need to be subtracted from the dataset. Rules would need to be established, such as whether the age summary should count the subject's age at first enrollment, at second enrollment or both.

As another example, adverse event (AE) incidence counts each subject only once within each system organ class and preferred term category as is standard in clinical trials. Additional programming would be required to link AE records from first enrollment and second enrollment for a re-enrolled subject in order to count him/her only once within each system organ class and preferred term.

Additional programming would be required also to link records for laboratory results and vital signs for re-enrolled subjects. All data listings would need reprogramming to link re-enrolled subjects as well.

A further complication is that several subjects re-enrolled in the study without the knowledge of the sponsor or study staff by visiting a different site and failing to disclose their prior participation in the VA-008 study. Such subjects may not have met the minimum 3-year interval between subsequent enrollments mandated in the protocol amendment.

Assessment:

Regarding a decision to amend the SAP, redesign the table and listing shells and reprogram the outputs, the following points were considered:

1. The primary objective of the VA-008 study is to ensure the safety of plasma donors vaccinated with ACAM2000 through implementation of risk factor screening procedures and collection of post-vaccination safety data. The reporting of study data in the clinical study report (CSR) does not impact subject safety, whether or not the outputs are modified for subject re-enrollment.
2. Scientifically, an argument can be made for treating re-enrolled subjects as independent subjects, particularly in the case of at least 3 years between vaccinations. Entry criteria for the study already require prior smallpox immunization. The protocol focuses on safety data surrounding each separate vaccination event from screening and vaccination through scab separation (by Day 35) and resolution/stabilization of any related AEs (through Day 90).
3. The study is ending this year and all tables and listings have already been programmed. The rework involved in modification of the outputs at this stage is considerable and the benefit minimal.
